Version No.	Date of preparation/revision	Prepared/revised by	Reasons
	proparation to vision		 Analysis items were changed in 2.9 and 2.20 13.3 Effectiveness 3.1.5.2, 3.1.7.2, 3.6 and 3.7 were newly added Analysis details was changed in 3.1.7.1 and 3.4 Analysis objective was changed in 3.5 Analysis item was changed in 3.5 Analysis target and objective were changed in 3.4.1
2.1	March 12, 2018.	[name]	■ 11. How to stratify data • "Partial Mayo score" was changed Changed from "≥6 and <9" to "≥6 and ≤9"

2. Definitions of terms and abbreviations

The terms and abbreviations used in this analysis plan are as follows:

Term and abbreviation	Definition
	Any untoward or unintended symptoms (including abnormal
Adverse event	laboratory findings), condition or illness which are not always
	related to Humira.
	Adverse events which occur from the first administration date of
Adverse events in the	Humira through Week 56 of administration (Day 1 + 392)
safety analysis period	Note that adverse events in discontinued cases should be the ones
salety analysis period	which occur from the first administration date of Humira through
	the final administration + 28 days.
	Adverse events which occur prior to the first administration date of
Adverse events not in the	Humira or beyond Week 56 of administration (Day 1 + 392).
safety analysis period	Note that adverse events in discontinued cases should be the ones
salety analysis period	which occur prior to the first administration date of Humira or
	beyond the final administration + 28 days.
Adverse reaction	Adverse events for which the causal relation with Humira cannot be
Adverse reaction	ruled out.
Adverse reactions in the	Adverse events which occurred in the safety analysis period and for
safety analysis period	which the causal relation with Humira cannot be ruled out.
Adverse reactions not in	Adverse events which occurred not in the safety analysis period and
the safety analysis period	for which the causal relation with Humira cannot be ruled out.
	It includes number of cases, mean, standard deviation, minimal
Summary statistics	value, 1st quartile value, median, 3rd quartile value and maximal
	value.
MedDRA/J	Medical Dictionary for Regulatory Activities / Japanese edition
SOC	System Organ Class in MedDRA/J
PT	Preferred Terms in MedDRA/J
LLT	Lowest Level Terms in MedDRA/J
IGRA test	Interferon gamma release assay
Partial Marya caara	Total of stool frequency sub score, rectal bleeding sub score and

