4.3. Target sample size for the survey

1500 patients

<Rationale for the sample size>

1. As this survey is conducted in the clinical settings, we expect that the patients with a treatment history with anti-TNFα drugs may be highly observed. Given that the registration of such patients can increase the dropout rate compared to that of the relevant domestic clinical studies, we calculated that the dropout rate would reach 70% at Week 52. Next, given that the number of patients whose CDAI of the effectiveness endpoint was not

provided in the all-case survey for Crohn's disease accounted for approximately 30%, we need 1500 patients with 30% remission rate, $\pm 5\%$ estimated accuracy of 95% CI and under the conditions where 30% of Mayo score are not assessable (Table 1).

Table 1: The number of patients and accuracy calculated based on the dropout rate

Dropout rate 70%				
C1-	After	Mayo score Number of	At Week 52 Remission rate	
Sample size	Week 52 Sample	patients for	30%	Accuracy
	size	assessment	95%CI	
500	150	105	21.2-38.8	$\pm 8.8\%$
1000	300	210	23.8-36.2	±6.2%
1500	450	315	24.9-35.1	±5.1%
2000	600	420	25.6-34.4	±4.4%

The number of cases with Mayo score provided was calculated as 70% of the total number of patients after Week 52 (i.e., 30% of Mayo score is not provided).

 Next, we examined the accuracy of the remission rate where the number of patients was 1500 as mentioned above with/without treatment experience of anti-TNFα drugs (Table 2).
 We set the following conditions for the accuracy examination:

The all-case survey data in Crohn's-disease patients who used Humira showed that 80% of the patients had been treated with anti-TNF α drugs while 20 % had not. Given that there were many patients who could not benefit from an anti-TNF α agent of prior medication awaiting right after the indication of Crohn's disease was approved, we expect that the same percentage of patients can be enrolled in this survey, too. In this regard, we decided to adopt the similar ratio for the anti-TNF α drug use in this survey and have the patients with and without the treatment history of the drug in an 8:2 ratio.

We set the remission rate of Mayo score at Week 52 in the patients without anti-TNF α drug history as 30% based on the percentage used to estimate the above 1500 patients and in the patients with the history as 10% based on the data in an overseas clinical study (M06-827 Study).

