10.3. Effectiveness analysis

Data name	Derivation and calculation methods
General improvement	Use what has been provided in "general improvement rate (primary
rate	physician's assessment" of the survey form.
	Partial Mayo score + endoscopic finding score
Mayo score	* Only the survey forms with all the scores assessed are calculated (if any
	unassessed scores are included, they are excluded from calculation)
Remission of Mayo	It should be calculated as 1 or less if the Mayo score is 2 or below and a
score	sub-score.
	Stool frequency score, rectal bleeding score and physician's global
Dontiel Mayo goons	assessment
Partial Mayo score	* Only the survey forms with all the scores assessed are calculated (if any
	unassessed scores are included, they are excluded from calculation)
Remission of partial	It should be calculated as 1 or less if the partial Mayo score is 2 or below
Mayo score	and a sub-score.
	Partial Mayo score at every assessment decreases by 2 points or more and
	by 30% or more in comparison to the partial Mayo score when
Improvement of	administration was started. In addition, at least one of the following
partial Mayo score	conditions shall be met.
(responder)	•Rectal bleeding score has been decreased by at least 1 point since the
	administration was started.
	• Rectal bleeding score is ≤1.
Endoscopy results	Use what has been provided in "endoscopic findings" of the survey form.

11. How to stratify data

Data	How to stratify
Dosage and	160mg→80mg→40mg once every two weeks and no changes thereafter,
administration	other
	The first administration to <week (1-28="" 4="" administration,="" days)<="" of="" td=""></week>
	≥Week 4 of administration and <week (29-56="" 8="" administration="" days)<="" of="" td=""></week>
	≥Week 8 of administration and <week (57-168="" 24="" administration="" days)<="" of="" td=""></week>
	≥Week 24 of administration and <week (169-336<="" 48="" administration="" of="" td=""></week>
Dose period	days)
	≥Week 48 of administration and ≤Week 52 of administration (337-365
	days)
	Unknown
	* when the first administration is counted as 1.
	≥1 and ≤4,
D	≥5 and ≤12,
Dosing frequency	≥13 and ≤24,
	≥25
	≥40mg and ≤500mg,
Total dose	≥501mg and ≤1000mg,
	≥1001mg
Reason for	Development of adverse event, lack of effectiveness, patient's wish, no
discontinuation	visit, others, multiple answers are acceptable
Reason for	Treatment/surgery, pregnancy, concern about the onset of adverse events,

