12.4. Assessment period for partial Mayo score

Time allowance of assessment period with the first administration date of Humira as 1 is as follows:

Assessment period	Time Allowance(Day)
At the first administration	-14 ~ 1 (scheduled date: 1)
Week 4 of administration	15 to 42 (scheduled date: 29)
Week 8 of administration	43 to 70 (scheduled date: 57)
Week 16 of administration	98 to 126 (scheduled date: 112)
Week 24 of administration	155 ~ 183 (scheduled date: 169)
Week 52 of administration	337 ~ 393 (scheduled date: 365)
At discontinuation	The final administration date of Humira + 14 (scheduled date:
	the final administration date of Humira)
At final assessment	Data for the final assessment period among the assessment
	applicable to the Time Allowance of each assessment period.

The data for analysis should derive from the one the closest to the scheduled date within Time Allowance. If there are more than one data dated on the same day, select the higher value.

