In addition, prepare a line plot to describe the percentage to the target patients among the patients who achieved a remission per assessment period.

X-axis: assessment period (in week)

Y-axis: remission rate (%)

Note: Follow "12.4 Assessment period for partial Mayo score" for Time Allowance of assessment period.

The analysis covers only the patients with the assessment applicable to Time Allowance of the first administration and each assessment period.

For the confidence interval, use the Clopper-Pearson's confidence interval.

Refer to "10.3 Effectiveness analysis" for the calculation method and remission rate.

NRI: when it is unknown whether the remission is achieved, impute the data without remission.

"3.1.7.1 Remission rate at Week 52 in patients who achieved a remission at Week 8 of administration based on partial Mayo score"

Patients for analysis: Patients in the effectiveness analysis group (the patients who did not achieve a remission when the administration was started but achieved the remission at Week 8 of administration in partial Mayo score)

Analysis objective: to show the remission rate of partial Mayo score at Week 52 of administration in patients in the analysis group.

Analysis items: calculate the number of target patients, the percentage to the number of patients who achieved a remission at Week 52 of administration and the target patients, and the confidence interval of the remission rate. (calculate them in both Observed Case and NRI patterns)

Note: the patients for analysis should have partial Mayo score at the first administration and Week 8 of administration and achieved a remission at Week 8 of administration except those who had already achieved a remission in partial Mayo score at the first administration.

Follow "12.4 Assessment period for partial Mayo score" for Time Allowance of assessment period.

For the confidence interval, use the Clopper-Pearson's confidence interval.

"3.1.7.2 Remission rate at Week 52 in patients who achieved the response as an index of partial Mayo score at Week 8 of administration"

Patients for analysis: Patients in the effectiveness analysis group (the patients who achieved a response at Week 8 of administration in partial Mayo score)

Analysis objective: to show the remission rate of partial Mayo score at Week 52 of administration in patients in the analysis group.

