Analysis items: calculate the number of target patients, the percentage to the number of patients who achieved a remission at Week 52 of administration and the target patients, and the confidence interval of the remission rate. (calculate them in both Observed Case and NRI patterns)

Note: the patients for analysis should have partial Mayo score at the first administration and Week 8 of administration and be a responder at Week 8 of administration.

Follow "12.4 Assessment period for partial Mayo score" for Time Allowance of assessment period. For the confidence interval, use the Clopper-Pearson's confidence interval.

Definition of responder: partial Mayo score at every assessment decreases by 2 points or more and by 30% or more. In addition, at least one of the following conditions shall be met.

- Rectal bleeding score has been decreased by at least 1 point since the administration was started.
- Rectal bleeding score is ≤ 1 .

"3.2 General improvement rate"

Patients for analysis: patients in the effectiveness analysis group

Analysis objective: to show the general improvement rate at Week 52 or at discontinuation of administration

Analysis item: calculate the number of patients in the analysis groups.

For the general improvement rate at the final observation which was calculated according to "12.5 Assessment period of general improvement rate", calculate the percentage to the number of patients and the patients in the analysis group per "general improvement rate" and "detailed classification for patients with an effective or better result in general improvement rate" defined in "11 How to stratify data".

"3.4 Aggregation for effectiveness per patient background factor (general improvement rate)" Patients for analysis: patients in the effectiveness analysis group

Analysis objective: to show the effectiveness rate of the general improvement rate at Week 52 or at discontinuation of administration as the primary endpoint and analyze the factors.

Analysis items: calculate the number of patients, the percentage to the number of patients with an effective (markedly effective + effective) in general improvement rate and all patients, the

percentage to the number of patients with an ineffective result in general improvement rate and the number of all patients, the tests for effectiveness (Fisher's exact test for nominal-scale factors and Man-Whitney's u test for ordinal-scale factors) per the following patient background factor.

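### NRI Table 3.1.5.2 keeps the observed-case restriction, so dropouts leave the denominator before they can be counted as non-remitters

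*SAP*

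**What the plan says.** SAP 13.3 plans two tables of partial Mayo remission by assessment period. They share the same nominal population (the effectiveness analysis group), items, McNemar test, Clopper-Pearson interval and line plot. Table 3.1.5.1 is labelled Observed Case and Table 3.1.5.2 is labelled NRI.

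The Notes to both tables contain this sentence, word for word: "The analysis covers only the patients with the assessment applicable to Time Allowance of the first administration and each assessment period". The Note to 3.1.5.2 then adds one line that 3.1.5.1 lacks: "NRI: when it is unknown whether the remission is achieved, impute the data without remission".

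Four other places bear on the point:

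- SAP 10.3 calculates a partial Mayo score only when every sub-score was assessed.
- SAP 9.1 rules out imputation except where an item in Chapter 10 or later defines it. The NRI line is therefore permitted, and it is the only authority for imputing in this table.
- Tables 3.1.7.1 and 3.1.7.2 also have an NRI version ("calculate them in both Observed Case and NRI patterns"), but they ask for less: "the patients for analysis should have partial Mayo score at the first administration and Week 8 of administration". No Week 52 score is required to enter them.
- The revision history in SAP section 1 records, for version 2.0, "3.1.5.2, 3.1.7.2, 3.6 and 3.7 were newly added". The NRI table was a deliberate addition.

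**The concern.** The two lines in the Note to 3.1.5.2 work against each other. NRI exists to keep patients without a score in the denominator as failures, and the restriction sentence takes those patients out. The SAP does not say which line prevails, nor which patients form the denominator if the NRI line does.

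The sample-size rationale in SAP 4.3 states "we calculated that the dropout rate would reach 70% at Week 52", so at the last time point most patients would be affected. Table 3.1.5.2 is the only NRI remission table for the whole effectiveness group: none is planned for the full Mayo score, and 3.1.7.1 and 3.1.7.2 cover only Week 8 remitters or responders. Under one table title, two programmers could report very different remission rates, each with a confidence interval and a test, in a document that serves the regulatory report and re-examination. A reader who sees the NRI label would assume that dropouts had been counted as failures.

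**Working it through.** **What the wording allows.** Take a patient in the effectiveness group with a baseline partial Mayo score and consider Week 52 (window Day 337 to 393, SAP 12.4).

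| Patient at Week 52 | Table 3.1.5.1 | Table 3.1.5.2, literal reading | Table 3.1.5.2 if NRI is effective |
|---|---|---|---|
| Complete in-window score | counted as observed | counted as observed | counted as observed |
| In-window form, a sub-score missing | out (10.3) | out under 10.3; on a lenient reading, imputed as non-remission | non-remission |
| No in-window assessment (dropout or missed visit) | out | out (restriction sentence) | non-remission |

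On the literal reading, NRI can change at most the middle row. Dropouts are removed on either literal or lenient reading.

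**Inputs for scale** (Protocol section 2 and SAP 4.3, Table 1): N = 1500, dropout 70%, Mayo score not assessed in 30% of those remaining, remission 30%. These were set for the full Mayo score. The documents give no missingness figure for the partial score, so what follows is an illustration.

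**The plan's own figure.** Assessed n = 1500 × 0.30 × 0.70 = 315. Half-width = 1.96 × √(0.3 × 0.7 / 315) = 5.06 percentage points, so the interval is 24.9 to 35.1%. This matches Table 1. The other three rows (105, 210 and 420 assessed) also reproduce.

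**Week 52 rate under each reading.** Remitters = 0.30 × 315 = 94.5. Clopper-Pearson intervals, the method the SAP names, use a whole count of 94 (135 in the last row).

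| Reading | Rate | 95% CI | Imputed |
|---|---|---|---|
| As written (same as observed case) | 94.5/315 = 30.0% | 24.8 to 35.2 | 0 |
| Lenient: all 450 − 315 = 135 unassessed assumed to have incomplete in-window forms | 94.5/450 = 21.0% | 17.2 to 24.9 | 135 |
| NRI, all 1500 with a baseline score | 94.5/1500 = 6.3% | 5.1 to 7.6 | 1500 − 315 = 1185 |
| NRI, dropout the only missingness (0.30 × 450 = 135 remitters) | 135/1500 = 9.0% | 7.6 to 10.6 | 1500 − 450 = 1050 |

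**Sensitivity.**

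- If only 70% to 85% of the 1500 are assumed to have a baseline score (1050 to 1275 patients), NRI gives 94.5/1050 = 9.0% to 94.5/1275 = 7.4%.
- If incomplete forms are assumed to be 2%, 5% or 10% of in-window assessments, the lenient reading gives 29.4%, 28.5% or 27.0%, close to the observed-case rate.
- In general, NRI rate = observed rate × share of the denominator with a usable in-window score. If 30%, 50% or 70% lack one, an observed 30% becomes 21.0%, 15.0% or 9.0%. The gap grows with attrition whatever the planning values.

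**The case against.** The strongest reply is that the SAP gives no order of operations. The NRI line is the one thing that distinguishes 3.1.5.2 from 3.1.5.1, the table is titled NRI and was added separately, and 9.1 sends imputation to the item's own definition. A sensible programmer would treat the restriction as carried-over text and let the specific rule govern. SAP 9.2 points the same way, since by default it keeps unknown and not-provided categories in percentage denominators.

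That reading is plausible and is probably what was intended, but the SAP does not state it. Section 9.2 leaves denominator details to Chapter 13, which is where the conflict lies. Even if the NRI line wins, the denominator is undefined: the whole effectiveness group, those with a baseline score, or those still under treatment.

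The second reply is that attrition shows up elsewhere. Table 3.4.1 reports partial Mayo remission at final assessment, Table 1.6.2 gives Kaplan-Meier continuation, Table 3.2 gives general improvement at Week 52 or discontinuation, and a reader could divide the remitters by the printed group size. All of this is true and limits the harm. None of these tables prints remission at each scheduled week with dropouts kept in, and the hand calculation is exact only if every patient has a baseline score.

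Third, the contrast of 30% with 6.3% rests on full-Mayo planning values and on all 1500 being in the effectiveness group with a baseline score. The 21% case assumes a cause of missingness that the documents do not support. These limits stand: the figures show scale and do not predict the result.

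Finally, this is a single-arm survey, and no sample-size figure or stated primary endpoint depends on 3.1.5.2. That bears on the weight of the point, not on whether the Note is wrong.

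**Conclusion.** The concern holds. As written, the Note to Table 3.1.5.2 removes the patients that NRI is meant to retain, so the table gives essentially the observed-case rate. It is not exactly the same rate on every reading, because an incomplete in-window form might still be imputed. The fault lies in the wording and does not depend on any planning value.

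The size does depend on them. On the illustrative Week 52 figures the rate is 30.0% as written, against 6.3% to 9.0% with NRI applied to patients with a baseline score. This range covers dropout as the only missingness and the assumed 70% to 100% with a baseline score. Actual partial Mayo missingness and the size of the effectiveness group are not in the documents. The NRI figure is a conservative convention and should not be read as the true remission rate.

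**What to change.** In the Note to Table 3.1.5.2, replace the restriction sentence with a rule to this effect: the denominator is every patient in the effectiveness analysis group who has a partial Mayo score in the first-administration window, and it is the same at Weeks 4, 8, 16, 24 and 52; an in-window score is used as observed; a missing or incomplete score in the window counts as not in remission. Apply NRI to those scheduled weeks only, not to the discontinuation and final-assessment rows. Print the number imputed at each week.

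This follows the form that already works in 3.1.7.1 and 3.1.7.2, where the later score is not an entry condition. Section 9.1 needs no change, and an NRI table for the full Mayo score is optional. Fixing the denominator is the essential part; printing the imputed counts helps the reader judge the result.

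The cost is one edited Note and one re-run table on data already collected. The drawback is a lower rate beside the observed-case one. NRI also counts as failures patients scored outside a window and patients who stopped because their condition improved, which SAP section 11 lists among the other reasons for discontinuation. Tables 3.1.5.1 and 3.1.5.2 should therefore be presented and read together.
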